6.2 Lifestyle Restrictions

- 1. Participants should refrain from donating blood or blood products from the time of the screening visit until 6 months following last dose of the study drug.
- 2. Participants should avoid excessive consumption of alcohol from screening visit until after follow-up visit is completed. Excessive consumption for this study is defined as more than 1 drink per day for female participants, or more than 2 drinks a day for male participants, on average.
- 3. Avoidance of products containing tetrahydrocannabinol (THC) and other recreational drugs.

6.3 Screen Failures

Screen failures are defined as participants who sign an informed consent to participate, but fail to meet eligibility criteria. A minimal set of data from screen fails is required to be maintained, including basic demographics, reason for screen failure, and any serious adverse events that occurred between the signing of the consent and time of screen failure.

Individuals who do not meet criteria for study participation (screen failure) may not be rescreened if the screen failure is due to non-eligibility due to plasma $A\beta(42)/A\beta(40)$ ratio assay, pTau217 assay, confirmatory CSF assay, or confirmatory amyloid PET scan. If the screen failure is due to not meeting the cognitive inclusion criteria (MoCA out of range), one rescreen may be allowed, at the investigators discretion, after 6 months if the MoCA score is above the cut-off, or if previous score is within range of amended MoCA range. If the screen failure is due to prohibited treatments (see Appendix H), or changes in medication, the individual may be rescreened if they subsequently discontinue use of the prohibited drug(s) and are then stable on all other medications for at least 30 days prior to rescreening, and previously collected data such as LP and/or MRI scans may be used for rescreening if the visit is within two months of said procedure. Other participants who fail screening procedures may be rescreened at the discretion of the investigator.

6.4 Withdrawal from Study

A withdrawal from the study shall be defined as withdrawing any time after being randomized into the double-blind treatment period, and before completing the events of the End of Treatment Visit. Participants who permanently discontinue use of the investigational product will be considered to be withdrawn from the study intervention, but may, if willing, complete other timepoint visits (such as EOT or F/U visits .

Participants may withdraw from the study at any time and for any reason. The investigator (or qualified designee) must document the reason for withdrawal in the participant file. If the participant withdraws consent for the continued use of data, biological or genetic samples, or imaging, the request must be received by the Sponsor, in writing, from the participant or legally authorized representative.

6.4.1 Withdrawal Procedures

If a participant prematurely discontinues treatment with the investigational product, the investigator must make every reasonable effort to perform the evaluations scheduled for the End of Treatment Visit as an Early Termination Visit. In the case where the participant permanently discontinues study medication between scheduled clinic visits, he/she should be requested to visit the clinic as soon as possible for the Early Termination Visit.

If a participant is lost to follow-up, every reasonable effort must be made by study personnel to contact the participant and study partner to inquire about the reason for discontinuation/withdrawal, and follow up with any unresolved AEs/SAEs. A minimum of 3 attempts at contact should be made, with all measures taken to contact the participant and information received during those attempts documented.

7 Treatments

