5.6 End of Treatment / End of Study Definitions

End of Treatment is the date of the last Visit or scheduled procedure for a participant, as listed in the Schedule of Events (Section 2)

End of Study is the date of the last Visit or scheduled procedure for the last participant randomized, as listed in the Schedule of Events (Section 2)

Every attempt should be made to follow participants through their final visit of the double-blind treatment phase and follow-up visit. If a participant discontinues the study prematurely for any reason, all reasonable attempts will be made to complete an Early Termination Visit, which will consist of the events listed for the End of Treatment Visit.

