7.5 Interruption of Treatment

Temporary interruption of treatment is allowed if a short-term treatment with an excluded medication is necessary, secondary to hospitalization, personal circumstances, or to evaluate the study drug impact on an uncertain AE, including but not limited to abnormal CBC with differential results (see Section 7.4), Grade 2 or higher AEs, and Grade 2 or higher abnormal laboratory values. Interruption of treatment should only be limited to significant events. If temporary interruption is due to an AE, it will be reported to the DSMB as part of the regularly scheduled aggregate reports. In such cases as above, reinitiation of treatment is at the trial physician(s) or qualified delegated clinician(s) judgement.

If a participant has to interrupt treatment for an extended period of time due to a significant medical condition or life event (such as greater than 7 dosing days off drug), it is possible to re-initiate treatment, and restarting the treatment will be at the trial physician's discretion, though it is suggested that if deemed necessary, consultation with the Sponsor may be done. Treatment re-initiation should occur as soon as possible and has to be confirmed by trial physician. Re-initiation of treatment will include a general safety examination by qualified medical personnel and safety labs. Restarting treatment after an interruption period that is greater than 10% of the trial length (i.e. 18 consecutive days) will be discussed between sponsor and trial physician before a final decision is made to re-initiate treatment at the discretion of the Sponsor. All information relating to interruption of treatment and re-initiation will be documented. Missed doses from the above category will not be considered in determining non-compliance.

7.5.1 Interruption of Treatment not related to short term treatment with excluded medication, hospitalization, personal circumstance or AE.

At the discretion of Principal Investigator, participants may request an interruption of treatment due to commitments such as travel obligations, for one block of time, up to 4 weeks in duration (28 dosage days). The study recording of interruption of treatment will allow for the addition of the time taken off to the study treatment period, up to the predetermined 28 dosage days. This interruption will not be factored into non-compliance, and a safety examination by study clinician is not required prior to resuming treatment.

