Participant: For individual participants, the **PI or Sub-I** may discontinue any participant if they reach grade 3 or 4 in any category, if laboratory results indicate blast cell appearance, or if they worsen in any of the cognitive tests by more than two standard deviations than would be normally expected from someone at their baseline measurements, or if they have any values that have exceeded greater than two times upper limits of normal for any trial measures. Participants are, of course, free to withdraw from the study at any time for any or no reason.

Specific participant stopping criteria for Absolute Neutrophil (ANC) count values are as follows:

• If a participants Absolute Neutrophil Count (ANC) is less than 0.5x10E3/uL (500 cells per microliter) at any CBC with differential safety blood draw post randomization, the participant will be monitored for potential infections over the course of 1 week until another CBC with differential is completed. If the ANC value does not demonstrate improvement (returned to a value above 0.5x10E3/uL), administration of the study drug to the participant should be discontinued.

Participants will be followed-up according to the study procedures as specified in this protocol up to the scheduled date of study completion, or up to recovery or stabilization of any AE to be followed-up as specified in this protocol, whichever comes last. If possible, and after the permanent discontinuation of treatment, the participants will be assessed using the procedures normally planned for the EOT visit with the treatment/placebo, including, but not limited to, LP (if chosen), imaging assessments and cognitive assessments. All cases of permanent treatment discontinuation should be recorded after confirmation.

The PI may also determine that a trial participant should no longer remain in the trial if there is evidence of uncontrolled hypertension. For an individual who has consented to volunteer for the trial, meets inclusion criteria and is enrolled, then begins the treatment phase of the trial, but who subsequently is determined to exhibit uncontrolled hypertension for more than 2 weeks (14 treatment days), the DSMB will be notified, within accepted timeframe, adverse events reporting protocols will be followed, and the following criteria will be used to determine whether the participant needs to be removed from the trial:

Inclusion Screening Criteria for hypertension:

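### Sections 5.6, 6.4, 6.4.1 and 8.4.5.3 disagree on when, and whether, the End of Treatment MMSE is taken after a participant permanently stops study drug

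*Protocol*

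**What the plan says.** Four sections of the protocol govern what happens after an early stop.

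- **6.4.1 Withdrawal Procedures.** When study drug is stopped prematurely, the investigator must make every reasonable effort to "perform the evaluations scheduled for the End of Treatment Visit as an Early Termination Visit". If the stop falls between clinic visits, "he/she should be requested to visit the clinic as soon as possible for the Early Termination Visit".
- **5.6 End of Treatment / End of Study Definitions.** A participant who leaves prematurely should "complete an Early Termination Visit, which will consist of the events listed for the End of Treatment Visit". The same section states that "End of Treatment is the date of the last Visit or scheduled procedure for a participant", with a reference to the Schedule of Events. It also asks for every attempt to follow participants through the last double-blind visit and the follow-up visit.
- **6.4 Withdrawal from Study.** A participant who permanently stops the product counts as withdrawn from the intervention and may, if willing, still attend other visits such as EOT or follow-up.
- **8.4.5.3 Data Monitoring Plan, stopping rules.** "Participants will be followed-up according to the study procedures as specified in this protocol up to the scheduled date of study completion", or until an adverse event has resolved or stabilized, whichever is later. The same paragraph adds that, if possible, "after the permanent discontinuation of treatment, the participants will be assessed using the procedures normally planned for the EOT visit", and gives no date for this.

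The endpoint that depends on these sections is in 4.5 and 9.2.2: the change in MMSE total score from Baseline to End of Treatment. Neither section names a week. The Schedule of Events places cognitive testing at Baseline, Week 12, EOT and Follow-up only.

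**The concern.** A site with a participant who stops at, say, Week 4 cannot tell from the protocol whether the MMSE is due then, at the scheduled Week 24/EOT date, or on both occasions. Nor can it tell whether the later visit is expected (8.4.5.3) or a matter of the participant's choice (6.4). If only the Early Termination Visit takes place, a participant who stops before Week 12 has no later MMSE.

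At stake is the interpretation of the only secondary endpoint. An analysis plan can define visit windows and choose a model, but it cannot supply a Week 24 score that was never collected. If the early score is then taken as the EOT value, a change over a few weeks is averaged with changes over about 24 to 25 weeks. In a declining disease that understates decline in whoever stopped early, and it leaves less time for any treatment effect to appear.

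**Working it through.** **Planned interval.** Section 5.4 gives 24 weeks of daily dosing: 24 × 7 = 168 days, which reproduces the protocol's maximum. The Schedule of Events gives EOT a tolerance of +2 to 10 days.

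- Planned EOT: 168 + 2 = 170 to 168 + 10 = 178 days, or 24.3 to 25.4 weeks after Baseline.
- Early Termination Visit: from a few days after Baseline upward, depending on when the participant stops.

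**Number affected.** The synopsis expects about 47 randomized and 42 completing: 47 − 42 = 5, and 5/47 = 10.6%. At 2:1, 47 is roughly 31 sargramostim and 16 placebo.

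**Effect of natural decline.** The protocol gives no MMSE decline rate. Assume a linear fall of 2 to 3 points over the planned interval, stopping times spread uniformly (so on average half the interval is unobserved), no treatment effect, and the early score used as the EOT value. Then

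spurious difference = decline × (stopping proportion on sargramostim − on placebo) × 0.5,

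where a positive value favours sargramostim.

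| Scenario | Arithmetic | Points |
|---|---|---|
| Equal stopping (10.6% each arm) | decline × 0 × 0.5 | 0 |
| All 5 on sargramostim (5/31 = 0.161) | 2 or 3 × 0.161 × 0.5 | +0.16 to +0.24 |
| All 5 on placebo (5/16 = 0.3125) | 2 or 3 × (−0.3125) × 0.5 | −0.31 to −0.47 |
| 20% vs 0%, or 30% vs 10% | 2 or 3 × 0.20 × 0.5 | +0.2 to +0.3 |

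The last row would be 0.2/1.8 = 11% to 0.3/1.8 = 17% of the 1.8-point pilot difference in 4.5. It needs more leavers than the protocol expects: 0.20 × 31 ≈ 6, or 0.30 × 31 + 0.10 × 16 ≈ 11, against about 5. The second and third rows are the extremes possible with 5 leavers. They have opposite signs.

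**Effect on a real benefit.** Suppose a benefit accrues linearly and a share q of participants, equal in both arms, is assessed at a fraction f of the planned interval. The mean effect is then multiplied by (1 − q) + q × f.

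- q = 5/47: f = 0.05 gives 0.90; f = 0.50 gives 0.95.
- q = 0.20: f = 0.05 gives 0.81; f = 0.50 gives 0.90.

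This works against sargramostim if the drug helps.

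**Whether the sections can be followed together.** A prompt Early Termination Visit and continued follow-up to the scheduled date are compatible in practice. The conflict is on two narrower points. First, later attendance is expected in 8.4.5.3 and voluntary in 6.4. Second, nothing says which MMSE is the EOT value when two exist, or that an early one is not. The 5.6 definition does not settle this: for an early stopper who does not return, the last visit is the Early Termination Visit, while for a completer the literal wording would point to the follow-up visit.

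**The case against.** The strongest reply is that the protocol never says the Early Termination MMSE is the EOT value. Section 5.6 fixes the content of that visit, not its label in the analysis. The visit has its own name, and 6.4 treats EOT as a separate occasion that people off drug may still attend. The Schedule of Events puts EOT after Week 24, and 5.6 refers to that schedule. A reader might infer that early scores are carried forward as the endpoint, but the text does not support so firm a reading; it only leaves the possibility open. How early scores enter the model belongs to the separate analysis plan announced in 9.3.1 and is not part of this point.

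A reader might also infer that early stopping spreads the assessment interval from days to about 29 weeks. It does not. The upper figure, 168 + 28 + 10 = 206 days or 29.4 weeks, arises only from the elective break in 7.5.1, which may "allow for the addition of the time taken off to the study treatment period". That concerns people who continue treatment. Early stoppers followed to schedule reach about 25 weeks.

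Finally, a reader might infer a bias in favour of sargramostim. The documents do not establish this. The dose holds in 7.4 and 7.5 are interruptions after which treatment may restart, not withdrawals. Section 4.4.2 reports that all 40 participants in the pilot's full-dose cohort completed, although dosing lasted only about three weeks.

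These replies remove any definite bias and the wide range. They do not remove the disagreement over whether a scheduled-date MMSE is expected after an early stop.

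**Conclusion.** The point holds as a conflict within the protocol about data collection. Sections 5.6, 6.4, 6.4.1 and 8.4.5.3 do not agree on the timing and expectation of EOT cognitive testing after permanent discontinuation. Read with 9.2.2, they allow an early stopper's MMSE change to rest on an interval much shorter than the planned 24 to 25 weeks, with no Week 24 value collected.

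About 5 of 47 participants are expected to be affected. The size and direction of any bias are unknown. It is about zero for natural decline under equal stopping, and under unequal stopping it may favour the arm with more early stoppers. Any effect that builds over time is diluted, to about 0.90 to 0.95 of its size at the expected rate. These figures depend on the assumed decline, stopping times, linear accrual and use of the early score as the EOT value; none of these comes from the protocol.

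The MMSE is secondary and safety is primary, so this does not threaten the main objective. It is worth correcting because the missing scores cannot be recovered later.

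**What to change.** Reconcile the four sections on assessment timing only, leaving every rule on dosing and on stopping treatment untouched:

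1. In 5.6 and 6.4.1, keep the Early Termination Visit but record it as its own visit, distinct from EOT.
2. In 6.4, in line with 8.4.5.3, state that participants who stop study drug but remain in the study are asked to return for the MMSE at their scheduled Week 12 and Week 24/EOT dates.
3. In 5.6, anchor EOT to the scheduled end of the treatment period instead of the participant's last visit or procedure.

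The cost is protocol wording, one visit label, and one or two assessment visits for about five people. Some will decline, and those who withdraw from the study altogether cannot be asked, so the gap will shrink but not close. The later EOT date after a 7.5.1 break is a separate matter that this change does not address.

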7.1 Treatment Administered

The investigational product (IP) in this study is defined as recombinant human GM-CSF (sargramostim) administered at a dosage of $178.57~\mu g/m^2/day$ by subcutaneous injection and its matching placebo. Sargramostim is commercially available from Partner Therapeutics, and will be obtained by the study Sponsor for this clinical trial. The sargramostim injections and placebo injections will be prepared by an unblinded UCH pharmacist or other qualified pharmacy personnel delivered to the blinded staff at location of the clinical visit. The IP and placebo will indistinguishable from each other.

The investigational product for the double-blind treatment period will be supplied as individual syringes sufficient for weekly dosing until their next scheduled dosing visit. In-clinic and at-home visit injections will be administered by the study partner with observation by a blinded study nurse or qualified designee for appropriate injection technique for the first 3 weeks, and at on site visits (Wk 6, Wk 12, Wk 18), with ongoing education as needed. If the study partner is unable to administer the once weekly in-person dose, qualified personnel may administer. Home injection administration to be completed by trained study partner with take home syringes for home administration. The IP will be placed into a hard-case for travel and storage and then within a travel container that will be monitored and that is designed to ensure temperature compliance. In conjunction with the take home syringes, an empty sharps container will be provided for the take home syringes to be placed into after they have been administered each treatment day. If sharps containers are filled they may be returned to the site and exchanged for empty containers as needed, otherwise the sharps container should be retuned at the end of the treatment. This cycle will be repeated every week for the 24 week double-blind treatment period. Additional details of these procedures are found in the Manual of Procedures.

The investigational product is to be stored in the home refrigerator of the participant. A temperature monitor will be provided, which will be reviewed every week to check for extreme temperature excursions. At the end of each dosing period (the projected number of dosing days between deliveries), if there are unused doses due to IP being held or form not being administered for any other reason, the participant and study partner will be instructed to dispose of the syringes in the sharps container, even if they are not expired, and to continue dosing only with the newly delivered doses.

The investigator or qualified designee is responsible for the following:

- explaining and training of the correct storage and use of the investigational product to the participant and her/his legal representative and her/his study partner (if different from LAR).
- verifying that the instructions are being properly followed
- maintaining accurate records of all investigational product dispensing and compliance.

For dosing modifications or titration, please refer to Section 7.4.

7.2 Method of Treatment Assignment

Participants who meet all criteria for enrollment will be randomized into sargramostim or placebo groups at Baseline Visit, at a 2:1 ratio. This enrollment ratio was determined using the sample size power analysis, as well as to maximize recruitment and minimize attrition. The randomization schedule will be enacted and maintained at the CU Research Pharmacy (CURP), which has policies and procedures in place that describe randomization and blinding. Briefly, the pharmacy has built and implemented an Excel spreadsheet that produces random number sets that may be used for simple, weighted, block (two-, four-, or six-sized), and stratified randomization. For blinding, the pharmacy staff includes the pharmacist manager and technician. The pharmacy staff has been involved in several clinical trials that require double blinding, and double dummy. The pharmacy is an independent entity, and has the ability to ensure and maintain blinding

in any regard so that the staff at the clinical site will not know which study participants are receiving the study drug or the placebo.

7.3 Blinding

As this is a double-blind study, to preserve the blind, a minimal number of study administration personnel will have access to the randomization table and treatment assignments before the study is deemed complete. These individuals will be designated by the Sponsor, [name], and kept in a log. The Data Safety Monitoring Board (DSMB) may be unblinded for safety evaluations or dose reduction decisions related to safety.

Additionally, preselected key personnel may have access to unblinded data to conduct pre-planned interim analysis for safety or for pre-planning activities for future clinical trials. Related, an external, independent Steering Committee will be established by the Sponsor to review data from the interim analysis to provide guidance on future trial planning.

Emergency unblinding for AEs may be performed through communication with the Investigational Pharmacy. This option can ONLY be used if the participant's well-being requires knowledge of the treatment assignment. The principal investigator holds the sole responsibility for determination of unblinding is warranted for medical management of the event. In such cases, the safety of the participant must always be the primary consideration for such determinations.

If an emergency unblinding occurs, the investigator must promptly document the decision and rationale, and notify the Sponsor and DSMB at earliest opportunity.

Decision to either discontinue the participant or continue with the study will rest with the Sponsor after consultation with the investigator and/or with the DSMB.

A list of all those who are unblinded to study treatment as the study progresses will be maintained and stored with the final documentation of the study.

